### **9.10. Randomization and Blinding**

This study is an open label study so therefore subject randomization does not apply for this clinical trial.

## 10. STUDY DRUG MATERIALS AND MANAGEMENT

### 10.1. Study Drug

The study medication for this study is ATI-50002 Topical Solution 0.46%. It is a clear, colorless to light pink solution. The inactive ingredients include: purified water, transcitol P, propylene glycol, PEG400, dimethyl sulfoxide (DMSO), kolliphor CS 20, benzyl alcohol, poloxamer 188, and povidone K30

**Table 5: Investigational Product**

STUDY MEDICATION INFORMATION	
Study medication name	ATI-50002
Dosage Strength	0.46%
Manufacturer	PMRS, Inc., Horsham, PA
Pharmaceutical Form	Topical Solution
Container	Amber Glass Bottle, 120 mL with screw cap
Storage Conditions	59°F to 77°F (15°C to 25°C)
Dose regimen	
Route	Topical
Frequency	Twice-daily
Duration of administration	52 weeks
Other supplies	Disposable, single-use droppers will be provided.

### 10.2. Study Drug Packaging, Labeling and Storage

The study medication must be used by the study subjects only. Investigational site staff will explain the application of the study medication to subjects.

Study medication will be provided by Aclaris Therapeutics, Inc. and labeled according to regulations. Study medications must be stored in a secure area with limited access under appropriately controlled and monitored storage conditions. Study medication should be stored at controlled room temperature 59°F - 77°F (15°C – 25°C). Subjects will be instructed to store the study medication in the original glass bottle (in the carton provided) at room temperature, away from heat, moisture, direct light, and to keep it from freezing and out of the reach of children.

The study medication will be supplied in amber glass 120 mL bottles. Disposable droppers with 1 mL calibration mark will be provided to the investigational sites for dispensing to enrolled subjects.

Study drug for this study is AT50002 Topical Solution 0.46%. The study medication will be supplied to subjects enrolled to the study on a monthly basis.

### **10.3. Study Drug Accountability and Disposal**

The Principal Investigator or designee is responsible for ensuring accountability for the investigational agent, including reconciliation of medications and maintenance of medication records. Upon receipt of study medication, the clinical site will check for accurate delivery and acknowledge receipt by signing (or initialing) and dating the documentation provided. One copy of this document will be returned to Aclaris Therapeutics, Inc. (or designee) and one copy will be maintained in the study file at the site. In addition, an accurate study medication disposition record will be kept, specifying the amount dispensed for each subject and the date of dispensing. This inventory record will be available for inspection at any time. At the completion of the study, the original inventory record will be available for review by Aclaris Therapeutics, Inc. upon request. Final medication accountability will be performed by the study monitor at the completion of the study and all used and unused study medication bottles will be returned to Aclaris Therapeutics, Inc. or designee for disposal.

### **10.4. Additional Clinical Supplies**

In addition to the study medication supplies, each site will be supplied with the following clinical supplies to conduct the study:

- Disposable dispensing droppers
- Canon Rebel T6i 18MP D-SLR
- Canfield IntelliFlash
- Stereotactic Head Device
- Dedicated laptop computer
- Canfield Capture Software
- Blue Drape Cloth
- Canfield VEOS SLR (18 MP)
- Canfield LED
- Secure Digital (SD) Memory Card
- Tattoo Machine and Ink
- Hair Clippers
- 4-inch curved scissors

## 11. ASSESSMENT OF EFFICACY

### 11.1. Target Area Hair Count (TAHC) and Target Area Hair Width (TAHW)

The primary efficacy endpoint of the study is the change from baseline in non-vellus (TAHC (hairs/cm^2)) and one of the secondary efficacy endpoints is the change from baseline in the cumulative TAHW. The subject's identified target area will be assessed for TAHC and TAHW by the Canfield trained and validated image analysis technicians who are blinded to the center/subject/visit/treatment information. Canfield Scientific, Inc. will supply all investigational sites with photography equipment, tattoo equipment, computer based scanners imaging software, and printers required to capture all global and macro photographs.

As described in Section 8.4, all subjects will be required to have a small permanent tattoo applied to their scalp to mark the center of the identified target area. Global and macrophotographs will be taken by the investigational study staff in accordance with the schedule of assessments. Refer to [Table 2](#) and [Table 3](#).

The Canfield supplied VEOS SLR camera will be used to take the macrophotographs of the subject's scalp. These images will be transmitted to Canfield for analysis using a computer assisted technique to assess the TAHC and TAHW.

Study staff will receive training from Canfield on the use of the photography equipment, scanners and imaging software in order to transmit all imaging data to Canfield.

### 11.2. Norwood-Hamilton and Sinclair Scales

Treating investigators will be required to rate the subject's level of hair loss at baseline based on the Norwood Hamilton Scale for male subjects and the Sinclair scale for women. In addition, at the protocol defined time-points, the Investigator will be required to use the appropriate scale to assess the change in hair growth in both male and female subjects.

### 11.3. Investigator Global Assessment and Subject Self-Assessment

Global photographs will be taken of the vertex scalp of male subjects and of the frontal scalp of both male and female subjects. These global scalp photographs will be used by the investigator and the subject to rate the subject's amount of hair growth at each protocol defined time-point.

After the global photographs are taken the investigator and the subject will use the current photos to rate the change in hair growth from the baseline visit (Visit 2). Both the investigator and the subject will record their assessment into the Canfield computer system. The following 7-point rating scale will be used:

**Table 6: 7-Point Rating Scale of Subjects Scalp Hair Based on Evaluation of Global Photographs**

Grade	Description
-3	Greatly decreased hair growth
-2	Moderately decreased hair growth

Grade	Description
-1	Slightly decreased hair growth
0	No change
+1	Slightly increased hair growth
+2	Moderately increased hair growth
+3	Greatly increased hair growth

## **12. ASSESSMENT OF SAFETY**

### **12.1. Safety Parameters**

Safety will be assessed throughout the study by the investigator or a designated and appropriately trained staff member.

#### **12.1.1. Demographic/Medical History**

During the screening visit (Visit 1), the investigator or designee will interview each subject to obtain demographic information including date of birth, sex at birth, Fitzpatrick skin type, race and, if appropriate, ethnicity. The investigator or designee will interview each subject to obtain medical history information related to all medical conditions, surgeries and disease states that, at screening: are ongoing, require concomitant therapy or are, in the opinion of the investigator, relevant to the subject's study participation. In addition, the medical history of women who are not of childbearing potential should reflect the reason e.g. post-menopausal for 1 year or greater, total hysterectomy. Information regarding the subject's prior treatments or therapies related to AGA must be documented along with the type of shampoo/conditioner the subject will use during the study.

#### **12.1.2. Vital Signs**

Vital signs will be measured at each visit during the study. The following items will be measured:

- Body temperature
- Pulse rate
- Respiration rate
- Blood pressure (systolic and diastolic) after the subject sits quietly for at least 5 minutes
- Height (at Visit 2 only)
- Weight (at Visit 2 only)

Any measure that is, in the opinion of the investigator, abnormal AND clinically significant (CS) must be recorded as history if found prior to the first study medication application, or as an AE if found after the first study medication application begins.

#### **12.1.3. Physical Examination**

The investigator or designee will perform a physical examination for all body systems (general appearance, examination of head, eyes, ears, nose and throat, respiratory, cardiovascular, abdominal, neurological, musculoskeletal, lymphatic and skin assessment) at Baseline (Visit 2) and end of study Week 30 (Visit 11)

#### **12.1.4. Electrocardiogram (ECG)**

Standard 12-lead ECGs will be performed by a qualified staff member at Screening (Visit 1), Visit 4 (Day 28) Visit 10 (Day 182) and Visit 11/Safety Follow up. The ECGs must be obtained

using a standard 12-lead ECG with a 10mm/mV amplitude, at 25mm/sec and a 5-10-second duration. To ensure a steady heart rate the subject must rest quietly in the supine position for at least 5 minutes prior to performing the ECG.

A central cardiology laboratory will provide ECG equipment, supplies and site training. In addition, the central cardiology laboratory will process ECGs received by the sites and report results via a secure study portal. The ECG results will be interpreted by a qualified health professional (evaluator) and the interpretation reported either directly on the tracing or in a separate report. The evaluator will interpret the results of every ECG and define the ECG as “normal” or “abnormal”. Variations such as minor ST changes (*i.e.*, <0.5mm depression) and early re-polarization are considered normal.

The investigator must review the evaluator’s interpretation of each subject’s screening ECG prior to Baseline (Visit 2). The investigator will review the evaluator’s interpretation of all ECG reports in a timely manner and comment on the clinical relevance of any result that is defined by the evaluator as abnormal.

Any abnormalities that are, in the opinion of the investigator, clinically significant, must be reported as history if found prior to the start of the first study medication application or as an AE if found after the start of the first study medication application.

If a subject’s ECG results meets the ECG withdrawal criteria that is outlined in section 7.3, the site staff must discontinue the subject from study medication and perform all protocol required assessments at the early termination/follow up visit.

#### **12.1.5. Pregnancy Tests**

Subjects who are WOCBP must have a negative serum pregnancy test result at Screening (Visit 1) to continue in the study, and a negative UPT at Baseline (Visit 2) prior to study entry. If the result of any post-treatment urine pregnancy test is positive, the subject will be withdrawn from the study and the subject’s pregnancy documented and followed. In addition, the investigator or designee will perform a urine pregnancy test for subjects who are WOCBP at monthly visits during the study.

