## 7.5. Schedule of Assessments

**Table 2: Schedule of Assessments-Initial 26 weeks of Treatment**

	Screening	Baseline	Treatment								Follow up Safety/Early Termination Visit 
	Visit 1	Visit 2	Visit 3	Visit 4	Visit 5	Visit 6	Visit 7	Visit 8	Visit 9	Visit 10	
			Week 3	Week 4	Week 8	Week 12	Week 16	Week 20	Week 24	Week 26	4 weeks post last application of ATI-50002
Treatment Day	-14 to 0	1	21	28	56	84	112	140	168	182	
Visit Windows	N/A	N/A	+/- 3 days	+/-4 days	+7 days	+/-7 days	+7 days	+/-7 days	+/-7 days	+7 days	+7 days
Informed Consent 	X										
Inclusion/Exclusion Criteria	X	X									
Demographics and Medical History	X										
Physical Exam 	X										X
Vital Signs 	X	X	X	X	X	X	X	X	X	X	X
Fitzpatrick Skin Type	X										
Prior Hair Treatment Assessment 	X										

	Screening	Baseline	Treatment								Follow up Safety/Early Termination Visit 
	Visit 1	Visit 2	Visit 3	Visit 4	Visit 5	Visit 6	Visit 7	Visit 8	Visit 9	Visit 10	
			Week 3	Week 4	Week 8	Week 12	Week 16	Week 20	Week 24	Week 26	4 weeks post last application of ATI-50002
Treatment Day	-14 to 0	1	21	28	56	84	112	140	168	182	
Visit Windows	N/A	N/A	+/- 3 days	+/-4 days	+7 days	+/-7 days	+7 days	+/-7 days	+/-7 days	+7 days	+7 days
Clinical Chemistry and CBC 	X				X		X		X	X	X
Quantiferon Gold 	X										
Total Iron Binding Capacity (TBIC), Serum Iron, Serum Ferritin	X										
Dihydrotestosterone (DHT), Testosterone, Estrogen, DHEA	X				X		X		X	X	X
Urine Pregnancy Test		X		X	X	X	X	X	X	X	X
Serum Pregnancy	X										
Serum PSA	X										
Thyroid Panel	X										
ECG	X			X						X	X

	Screening	Baseline	Treatment								Follow up Safety/Early Termination Visit 
	Visit 1	Visit 2	Visit 3	Visit 4	Visit 5	Visit 6	Visit 7	Visit 8	Visit 9	Visit 10	
			Week 3	Week 4	Week 8	Week 12	Week 16	Week 20	Week 24	Week 26	4 weeks post last application of ATI-50002
Treatment Day	-14 to 0	1	21	28	56	84	112	140	168	182	
Visit Windows	N/A	N/A	+/- 3 days	+/-4 days	+7 days	+/-7 days	+7 days	+/-7 days	+/-7 days	+7 days	+7 days
Norwood-Hamilton classification(males); Sinclair Scale (females)Assessment	X	X					X			X	X
Target Area Hair Identification and Tattoo application 		X									
Global Scalp Photograph 	X	X 			X 		X 			X 	X
Macro Scalp Photographs 		X			X		X			X	

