**Table 3: Schedule of Assessments – 6-month Extension Study**

							Follow up Safety/Early Termination Visit
	Visit 11	Visit 12	Visit 13	Visit 14	Visit 15	Visit 16	Visit 17
Treatment week	Week 30	Week 35	Week 39	Week 44	Week 48	Week 52	Week 56
Visit Windows	+7 days	+7 days	+7 days	+7 days	+/-7 days	+7 days	+7 days
Physical Exam 							X
Vital Signs 	X	X	X	X	X	X	X
Clinical Chemistry and CBC 			X	X		X	X

Dihydrotestosterone (DHT), Testosterone, Estrogen, DHEA			X			X	X
Urine Pregnancy Test	X		X	X	X	X	X
ECG			X				X
Norwood-Hamilton classification(males); Sinclair Scale (females)Assessment						X	X
Global Scalp Photograph			X 			X 	X
Macro Scalp Photographs 						X 	
Target Area Hair Count (TAHC) and Target Area Hair Width (TAHW) 						X	
Demonstration of study drug application 	X	X	X	X	X	X	
Dispensing of study medication 	X	X	X	X	X	X	
Investigator Assessment of Hair Growth			X			X	X
Subject Self - Assessment of Hair Growth			X			X	X

Local Skin Reaction Assessment	X	X	X	X	X	X	X
Adverse Events 	X						
Concomitant Therapies	X						

 A physical exam includes: general appearance, examination of head, eyes, ears, nose and throat, respiratory, cardiovascular, abdominal, neurological, musculoskeletal, lymphatic and skin assessment.

 Vital signs include: oral or ear temperature, blood pressure, heart rate, respiration rate.

 Serum chemistry panel to include: albumin, alk phos, ALT, AST, BUN, bicarbonate, calcium, chloride, creatinine, glucose, lactate dehydrogenase (LDH), phosphorus, potassium, sodium, total bilirubin, total protein, uric acid, total cholesterol, LDL, HDL triglycerides, CPK, and complete blood count including differential.

 Canfield staff will review all global photographs within 2 days of the photographs being submitted. If a re-take is required, Canfield will notify the site and the re-take photographs will need to be performed within 7 days of the visit.

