 Canfield staff will review all macro photographs within 2 days of the photographs being submitted. If a re-take is required, Canfield will notify the site and the re-take photographs will need to be performed within 7 days of the visit.

 Sites will take the macro photographs and transmit these to Canfield in order for the Canfield scientists to perform the Target Area Hair Counts and the Target Area Hair Widths. The TAHC and TAHW will be entered into the Canfield database.

 Sites will be required to review with each subject the proper application of the study medication and remind the subjects that they are only to wash their hair with the same shampoo/conditioner and maintain the same hair style throughout the study.

 Subjects will be dispensed bottles of study medication at each monthly visit. Study medication will be weighed prior to dispensing the medication to the subject and upon return of both used and unused bottles.

 All non-serious AEs will be collected from the time of first study medication application until the final study visit. Serious AEs will be collected from the time of consent through the final study visit.

 A final safety follow up visit will be conducted at week 56 (Visit 17). For those subjects that discontinue the study early, they must return to the clinic 4 weeks following the last study medication application for a final safety visit.

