### **12.4.2. Highly Effective Methods of Birth Control**

The Investigator or sub-investigator will discuss the potential risk factors associated with pregnancy and the importance of maintaining a highly effective method of contraception throughout the study with all WOCBP (for example, those which result in a low failure rate - *i.e.*, less than 1% per year- when used consistently and correctly). All WOCBP must use a highly

effective method of birth control during the study and for 30 days after the final application of study medication in a manner such that risk of failure is minimized.

Highly effective methods include:

- Combined (estrogen and progestogen containing) hormonal contraception associated with inhibition of ovulation:
  - oral
  - intravaginal
  - transdermal
- Progestogen-only hormonal contraception associated with inhibition of ovulation:
  - oral
  - injectable
  - implantable
- intrauterine device (IUD)
- intrauterine hormone-releasing system (IUS)
- vasectomized partner
- sexual abstinence

Vasectomized partner is a highly effective birth control method provided that partner is the sole sexual partner of the WOCBP trial participant and that the vasectomized partner has received medical assessment of the surgical success.

 Sexual abstinence is considered a highly effective method only if defined as refraining from heterosexual intercourse during the entire period of risk associated with the study treatments. The reliability of sexual abstinence needs to be evaluated in relation to the duration of the clinical trial and the preferred and usual lifestyle of the subject.

WOCBP must be on a highly effective method of birth control for the following timeframes prior to study entry:

- Implants (on a stable dose for  $\geq 90$  days)
- Injectables (on a stable dose for  $\geq 90$  days)
- Patches (on a stable dose for  $\geq 90$  days)
- Combined oral contraceptives (on a stable dose for  $\geq 90$  days)
- Intrauterine devices (inserted for  $\geq 30$  days).

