Prior to trial enrollment, WOCBP must be advised of the importance of avoiding pregnancy during trial participation and of the potential risk factors associated with pregnancy while in the study. The subject must sign an informed consent form documenting this discussion. During the trial, all WOCBP will be instructed to contact the investigator immediately if they suspect they might be pregnant (*e.g.*, missed or late menstrual period).

If a subject or investigator suspects that the subject may be pregnant prior to study medication administration, the study medication must be withheld until the results of a pregnancy test are available. If pregnancy is confirmed, the subject must not receive study medication and must be discharged from the study.

If, following study medication administration, it is determined that the subject may have been or was pregnant at the time of study medication exposure (including at least 2 days after study medication administration) the investigator must immediately notify the Aclaris Therapeutics, Inc. Medical Monitor and record the event on a pregnancy surveillance form. While not an AE or SAE, the investigator must report every pregnancy using a pregnancy surveillance form and follow the reporting procedures described for SAE reporting.

Protocol-required procedures for trial discontinuation and follow-up must be performed on the subject unless contraindicated by pregnancy (*e.g.*, x-ray studies). Other appropriate pregnancy follow-up procedures should be considered if indicated. In addition, the investigator must report to Aclaris Therapeutics, Inc.'s Medical Monitor on the pregnancy surveillance form, follow-up information regarding the course of the pregnancy, including perinatal and neonatal outcome. Infants should be followed for a minimum of six weeks.

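### Section 12.1.5 calls for a urine pregnancy test at monthly visits, but Table 3 leaves Visit 12 (Week 35) blank although drug is dispensed there

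*Protocol*

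**What the plan says.** Section 12.1.5 (Pregnancy Tests) requires a negative serum test at screening and a negative urine test at baseline for women of childbearing potential (WOCBP). For the rest of the trial it says that "the investigator or designee will perform a urine pregnancy test for subjects who are WOCBP at monthly visits during the study". It names no last visit and makes no exception. On the consequence of a result it says: "If the result of any post-treatment urine pregnancy test is positive, the subject will be withdrawn from the study".

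Table 2 (initial 26 weeks) marks the urine test at Visits 2 and 4 to 10 and at follow-up. It marks dispensing at Visits 2 and 4 to 10.

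Table 3 (extension) has seven visit columns. Its "Urine Pregnancy Test" row is marked at Visits 11, 13, 14, 15, 16 and 17, and the Visit 12 cell is empty. Its "Dispensing of study medication" row is marked at Visits 11 to 16, including Visit 12. Footnote 8, attached to that row, reads "Subjects will be dispensed bottles of study medication at each monthly visit". No footnote addresses the empty cell.

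Section 12.4.2 supplies a second route to detection: "all WOCBP will be instructed to contact the investigator immediately if they suspect they might be pregnant". It also requires highly effective contraception, which it illustrates by a failure rate of "less than 1% per year".

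**The concern.** Text and schedule give different instructions for the same visit. If Visit 12 is a monthly visit, Section 12.1.5 requires a urine test there and Table 3 does not show one. Sites commonly run visits from the schedule table, so two sites could treat the same woman differently at Week 35: one tests her, the other gives her about four more weeks of drug without a test.

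What is at stake is fetal exposure to a JAK inhibitor in a woman whom the protocol would withdraw if she tested positive. The number of women is small and other safeguards exist, so this is a question of schedule consistency with a safety consequence.

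**Working it through.** **Step 1. Compare the two rows.**

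| | Dispensing marked | Urine test marked at those visits |
|---|---|---|
| Table 2 | Visits 2, 4, 5, 6, 7, 8, 9, 10 (8 visits) | all 8 |
| Table 3 | Visits 11, 12, 13, 14, 15, 16 (6 visits) | 5; not Visit 12 |

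That makes 8 + 6 = 14 visits marked for dispensing, 13 of them with a test. Visit 3 (Week 3) also has no urine test, but no drug is dispensed there and a test follows at Week 4.

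**Step 2. Look for a design reason.** Visit 12 is an attended visit: vital signs, local skin reactions, application review and dispensing are all marked. It has no blood draw, but neither do Visits 11 and 15, and both carry a urine test. Nothing in Table 3 sets Visit 12 apart.

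**Step 3. Intervals between scheduled tests.** Days come from Table 2 and, for the extension, from week × 7. Windows are as printed. The shortest interval is the earliest later visit minus the latest earlier visit; the longest is the reverse.

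| Interval | Nominal days | With windows |
|---|---|---|
| V2–V4 | 28 − 1 = 27 | 23–31 |
| V4–V5 | 28 | 24–39 |
| V5–V6 | 28 | 14–35 |
| V6–V7 | 28 | 21–42 |
| V7–V8 | 28 | 14–35 |
| V8–V9 | 28 | 14–42 |
| V9–V10 | 14 | 7–28 |
| V10–V11 | 28 | 21–35 |
| **V11–V13** | **273 − 210 = 63** | **273 − 217 = 56 to 280 − 210 = 70** |
| V13–V14 | 35 | 28–42 |
| V14–V15 | 28 | 14–35 |
| V15–V16 | 28 | 21–42 |
| V16–V17 | 28 | 21–35 |

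Outside V11–V13 the longest interval is 35 days nominal and 42 with windows. The shortest possible V11–V13 gap (56) exceeds the longest possible gap elsewhere (42) by 14 days.

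**Step 4. Effect of a test at Visit 12.** Week 35 is Day 245, window +7. V11–V12 becomes 35 days (28–42) and V12–V13 becomes 28 days (21–35), both in line with the rest.

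**Step 5. Extra dosing for one affected woman.** If a pregnancy is detectable at Week 35 and nothing else reveals it before Week 39, the extra dosing is 28 days × 2 applications a day = 56 applications. With windows it is 21 × 2 = 42 to 35 × 2 = 70. These are upper bounds, because self-report would shorten them.

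**Step 6. How often this could happen.** A Visit 12 test gains time only for pregnancies that become detectable in the 35 days after Visit 11; earlier ones would be found at Visit 11. Expected number = women × annual rate × 35/365. The documents do not say how many women are WOCBP or enter the extension, so 12 and 6 are assumptions. The 1% rate is the Section 12.4.2 ceiling; 5% is an assumed value for imperfect use.

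| WOCBP in extension | 1% per year | 5% per year (assumed) |
|---|---|---|
| 12 | 12 × 0.01 × 35/365 = 0.012 | 0.058 |
| 6 | 0.006 | 0.029 |

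**The case against.** The strongest objection is that the conflict depends on a reading. Monthly visit is nowhere defined, and Visit 10 comes only two weeks after Visit 9, so dispensing and monthly spacing do not coincide exactly. The dispensing row is itself imperfect evidence: it marks Visit 16 (Week 52), when treatment ends, and Visit 10 dispensing applies only to women who continue. This much stands, and the count of 13 in 14 should not carry the argument alone. Visit 12 nevertheless remains the only exception whether or not Visits 10 and 16 are counted.

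A second objection is that Section 12.1 was written for 26 weeks and Table 3 is the later, extension-specific schedule. Sections 12.1.3, 12.1.4, 12.1.6 and 12.1.7.1 do still stop at Visit 11. Section 12.1.5 does not: its monthly tests run for the whole study, and Section 7.1 describes extension subjects as remaining on study. The objection weakens the conflict without removing it. If a nine-week gap was intended, neither the text nor a footnote says so.

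A reader might infer that a site following Section 12.1.5 would test before handing over drug at Week 35. The section does not support that. It fixes an order only at baseline, where the negative urine test must precede study entry; for monthly visits it is silent on order.

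The remaining safeguards are real: mandatory highly effective contraception, the instruction to report a suspected pregnancy immediately, and scheduled tests at Weeks 30 and 39. They limit the consequence but do not settle which instruction a site should follow.

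**Conclusion.** The inconsistency holds on the natural reading that Visit 12, a dispensing visit between Weeks 30 and 39, is one of the monthly visits. Its size is a 63-day interval between scheduled tests (56 to 70 with windows) for sites that follow Table 3, and up to about 28 days (21 to 35) of further dosing in a woman whose pregnancy was detectable at Week 35 and who did not report it.

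This is a minor safety correction. The expected count is about 0.006 to 0.012 pregnancies at the protocol's 1% ceiling, with 6 to 12 women assumed. Twelve is the approximate planned number of women and not a fixed ceiling on enrolment.

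A reader might go further and conclude that the protocol permits dosing at Week 35 without a test, or that participants face a sizeable risk. The documents support neither. Section 12.1.5, read naturally, still requires the test, and harm per exposure cannot be sized because the documents give no reproductive-toxicity or systemic-exposure data. The efficacy analysis is not affected.

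**What to change.** Mark the Urine Pregnancy Test row at Visit 12 (Week 35) in Table 3.

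Doing that test before drug is dispensed is a sensible recommendation, but it would be an addition, since Section 12.1.5 does not state it for monthly visits.

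The cost is one mark at the next amendment and one urine test for each WOCBP in the extension (about 12 women at most on the planned numbers), at a visit they already attend.
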